**Rapid Testing and Dried Blood Spot Quality Control:**

*Research Assistant B* will follow the relevant items on the *Checklist for Good Testing Practices*

 [https://www.cdc.gov/clia/Resources/WaivedTests/pdf/FINAL\\_Self-Assessment%20Checklist%20for%20Good%20Testing%20Practices.pdf](https://www.cdc.gov/clia/Resources/WaivedTests/pdf/FINAL_Self-Assessment%20Checklist%20for%20Good%20Testing%20Practices.pdf)

Brown University IRB Amendment Approval: 11/09/2021  
Brown University IRB Amendment Approval: 12/13/2021

to ensure all procedures are followed accordingly.

- Prior to conducting urine screens, all *Research Assistants* will complete an online CLIA Testing Best Practices training through the Centers for Disease Control and Prevention, *Ready? Set? Test! Patient Testing is Important. Get the Right Results. CE Course Number: WB2639*.
- Testing will be done in accordance with the manufacturer's guidelines, and the Centers for Disease Control and Prevention guidelines: *Good laboratory practices for waived testing sites.*MMWR 2005;54(No. RR-13).
- Dried blood spots collected using capillary finger-stick methods will be undertaken according to the *WHO guidelines on drawing blood: best practices in phlebotomy* (ISBN: 978 92 4 159922 1) and the *WHO manual for HIV drug resistance testing using dried blood spot specimens* (WHO reference number: WHO/HIV/2012.30).
- Prior to collection of dried blood spots, all *Research Assistants* will complete "Qualified Professional Testing Counselor" training as required in the state of Rhode Island.

### **3.1.c Participant Population**

The target population for this trial are adults aged 18 to 65 who are at risk of overdose due to consumption of IMF-contaminated illicit substances.

Eligibility Criteria: Participants will be enrolled in the RAPIDS trial if they are: (a) 18 to 65 years of age; (b) reside in Rhode Island; (c) are able to complete interviews in English; (d) are able to provide informed consent; and (e) self-report past 30 day use of heroin, illicit stimulants (e.g., powder cocaine, crack, methamphetamine), counterfeit prescription pills, or injection drugs, regardless of treatment status.

These criteria are consistent with our pilot study, and were selected to capture a population of PWUD who are at risk of being exposed to IMF-contaminated illicit substances, based on our prior epidemiologic research and other studies. We expect that the racial and ethnic composition of our target population will be similar to that of the samples recruited for our prior research studies involving the target population (approximately 60% white, 20% Black or African American, and 15% mixed race). We also anticipate that males will be over-represented among our target population (approximately 60%). Section **3.1.d** below, outlines the methods for ensuring wide recruitment, in addition to partnering with community-based organizations to increase enrollment.

We will exclude: persons who report exclusive misuse of medications obtained from a physician or diversion from someone else's prescription (e.g., family members), since these sources are unlikely to be associated with IMF exposure.

---

<https://www.cdc.gov/mmwr/PDF/rr/rr5413.pdf>

Brown University IRB Amendment Approval: 11/09/2021  
Brown University IRB Amendment Approval: 12/13/2021

### 3.1d. Recruitment, Enrollment, Randomization, and Retention procedures

Recruitment: Consistent with our previous research, we will employ a combination of field-based recruitment techniques (e.g., targeted canvassing, word of mouth) and Internet-based advertising to recruit potential study participants. Our team successfully identified locations for targeted canvassing in our pilot work. Project staff will conduct outreach and post study flyers in public and semi-public community venues (e.g., bus stops, parks, community organizations, drop-in centers, shelters, needle and syringe programs) in which PWUD are known to congregate. In addition, a recent spatial analysis conducted by our study team found that, between 2014 and 2017, fentanyl-involved overdose deaths have occurred in 37 of 39 municipalities in RI. As such, recruitment will occur throughout Rhode Island; for example, we will purchase advertising on bus routes and radio stations that operate throughout the state. Internet-based recruitment will include advertising on drug information websites used by PWUD (e.g., erowid.org, drugs-forum.com), online classifieds (Craigslist), and social media websites (e.g., Facebook), as well as Today at Brown.

[figure not shown]
Communication resources: Sufficient iPhones, so that each research assistant has access to one, will be purchased through Brown University's Computing & Information Services (CIS) to be used by research assistants. Throughout the study, study cell phones will only be used by authorized research assistants and staff members involved with participant communication. At the start and end of the day, the primary cell phone will be turned on or off and be checked in and out of a locked desk within the study office. Each cell phone will be encrypted using a custom alphanumeric code, with settings enabled to destroy all data on the phone after 10 failed attempts. The second cell phone will be also be used for field visits as necessary.

Both cell phones used in the study will be insured to include repairs through accidental damage, replacement, and theft protection. In addition, all cell phones will be installed with an application which allows for the remote GPS tracking of each device. Each cell phone will have encrypted backups of information stored on iCloud.

In the event that a cell phone is lost, stolen, or otherwise not returned, the iPhone will be remotely wiped of data. At the end of the study, all encrypted cell phone data will be destroyed and all cell phones will be wiped of data and returned to Brown University's Computing & Information Services (CIS).

Enrollment and assessment will occur in two stages: First, potential participants will text message, email, or call a study hotline, at which point a study staff member will screen for eligibility. If eligible, the staff member will then schedule an interview at the Brown University School of Public

Figure 3: Study Recruitment

Brown University IRB Original Approval: 4/18/2019

Brown University IRB Amendment Approval: 11/22/2019

Brown University IRB Amendment Approval: 8/10/2020

Brown University IRB Amendment Approval: 10/15/2020

Brown University IRB Amendment Approval: 02/26/2021

Brown University IRB Continuing Review Approval: 03/18/2021

Brown University IRB Amendment Approval: 06/15/2021

Brown University IRB Amendment Approval: 09/01/2021

Brown University IRB Amendment Approval: 10/05/2021

Brown University IRB Amendment Approval: 11/09/2021

Brown University IRB Amendment Approval: 12/13/2021

Motivational interviewing booster sessions

Additional fentanyl test strips distributed as needed

Key Assessment visits

Additional fentanyl test strips distributed as needed

Health. At this time, all assessments will occur at our study offices, which are centrally located and easily accessible to members of the study population. In some circumstances, the interviews may occur at a semi-private location outside of BUSPH (ex. Public library study rooms, clinics or other community partner agencies) (see **Attachment I**, Safety Protocol, for field-based safety measures).

Randomization: Randomization: Participants will be randomized 1:1 using a randomization table generated in SAS by the study's Biostatistician, which will be operationalized using the Randomization Generator Module in REDCap. Randomization will be assigned during the baseline visit. Intervention allocations will be maintained in REDCap by authorized users only, such as the study Statistician, and revealed only through REDCap by prompts during the baseline survey visit and post-baseline visits (See **Figure 3**).

Blinding: Staff conducting the baseline and follow- up assessments will be blinded to intervention assignment until completion of the STUDY ENROLLMENT INFORMED CONSENT FORM at the Baseline visit. Intervention allocations will be maintained in REDCap by authorized users only, such as the study Statistician, and revealed only through REDCap by prompts during the baseline survey visit and post-baseline visits.

Retention: To maximize retention, we will employ retention strategies that are effective with PWUD.

For example, we have found that text messages are the preferred mode of communication: over 95% of participants in our pilot study owned a cell phone and used it daily. We have included study cell phones in the budget so project staff can text participants at least monthly to update contact information. Additional retention strategies to be employed include: (1) maintaining a tracking database of contact information (e.g., phone numbers, email addresses, social media handles, physical addresses for sending appointment reminder postcards); (2) conducting regular outreach in areas that participants are known to frequent; (3) providing honoraria for all study visits; (4) providing free parking to participants visiting the study office by validating garage parking passes; (5) searching the public RI Department of Corrections database to determine if a participant is incarcerated for a period of longer than 90 days, at which point they will be withdrawn from the study. These strategies were used effectively in our RAPIDS pilot study, resulting in a 90% follow-up rate.

**3.1 e How confidentiality of data will be maintained (where data is kept, who has access to it, and how it is kept secure).** The Principal Investigator, [name] is ultimately responsible for data safety and monitoring of the study. This process will be monitored on a weekly basis by his team, including the Project Director, Data Analyst, and Senior Research Assistant, with quarterly updates to the entire team of Co-Investigators. The project team will be responsible for ensuring that all policies and processes outlined in the Data Use Agreement (with Rhode Island Department of Health, **Attachment E**) are followed accordingly, and that data are

 <http://cri.uchicago.edu/wp-content/uploads/2015/12/REDCap-Randomization-Module.pdf>

transferred and shared on the agreed-upon timeline.

This study includes a Data and Safety Monitoring Board (DSMB) and Plan (DSMP). The DSMB will meet on a semi-annual basis with the PI and Project Director to review the DSMP and protocol adherence (see **Attachment F**). The DSMB will also review any adverse or severe adverse events as outlined in the DSMP.

**Stronghold computing environment:** We will obtain a central storage service hosted by Brown University's Computing & Information Services (CIS) Stronghold project (see **Attachment G**, Stronghold MOU). Stronghold is a HIPAA-aligned, secure computing environment developed for housing, sharing, and analyzing sensitive data. The project's Data Analyst will oversee the database architecture, dataset storage, and all input/output (i.e., RIDOH data transfer) regulations. Stronghold is highly secure computer and storage Windows-exclusive environment for research needs that involve very sensitive data needing special handling, data usage agreements, etc.

**All Stronghold users must:** Be approved by the Principal Investigator, authorized in writing to Brown University Computing & Information Services (CIS), and:

- complete appropriate training for working with sensitive data (e.g. CITI training);
- be in compliance with all relevant Institutional Review Board protocols;
- be in compliance with any data use agreements or other agreements governing the use of the data stored on Stronghold;
- complete an on-boarding process led by the Principal Investigator or Senior Research Assistant, which includes a review of data security protocols and a guided walkthrough of accessing the Stronghold virtual environment.

**Data Transfers** – there are select methods to import data, including but not limited to:

- Select Rhode Island state agencies and other offices using a secure VPN tunnel
- Encrypted USB drives
- Secure transfer through firewall exception
- Import and export servers

For the proposed project, we will conduct and automate secure data transfer of administrative overdose records with RIDOH on a monthly basis (according to the timeline outlined in our existing data use agreement, see **Attachment E**). Any matching between personally identified data sources is done within a secured area prior to any data (de-identified) being exported. After the baseline survey, a separate consent procedure will be used to gain permission to obtain information regarding overdose events (to be submitted as a future amendment, upon RIDOH approval). To conduct the probabilistic, confidential data linkage with the RIDOH administrative surveillance records, we will first create an encrypted, password-protected file containing the linkage variables (e.g., sex, date of birth, zip code of residence). We will link these surveillance datasets with participant data using a probabilistic linkage with the following combination of identifiers: first and last name, date of birth, and sex. To conduct the probabilistic match, we will use The Link King software. All linkages will be conducted within

Brown University IRB Amendment Approval: 11/09/2021  
Brown University IRB Amendment Approval: 12/13/2021

Stronghold, a HIPAA-aligned secure computing environment at Brown University. Matched records will then be transferred to and stored on computers at the CEEH using secure data-transfer and storage protocols.

Survey data will be collected on password-protected tablets and computers within the Centers for Epidemiology and Environmental Health (CEEH) at the Brown University School of Public Health. The REDCap™ platform exceeds patient confidentiality and data security requirements for clinical trials, and are both HIPAA compliant and fully validated for FDA 21 CFR Part 11.

REDCap™ is a secure and web-based platform that allows input data from anywhere with secure web authentication, data logging, and Secure Sockets Layer (SSL) encryption. For remote data entry during field-based interviews, staff will be given iPads with data connectivity that allow for direct and secure data entry into REDCap™.

Access to project data will be restricted to individuals who are authorized to work on the project. Access to data with identifiers is further restricted to the Systems/Data Manager alone. Data are de-identified before analytic files are created, providing an additional level of protection.

Furthermore, Center employees have signed an oath of confidentiality, and its violation is sufficient grounds for immediate termination. All of our research assistants are CITI certified, and will receive comprehensive orientation and intervention training for this research study prior to interacting with participants or study data.

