**ARM ASSIGNMENT [PIPE FROM SCREENER, RA SEES ARM ASSIGNMENT]**

- ARM 1 (Control)**
- ARM 2 (Experimental)**

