Given the nature of our eligibility criteria, the most severe adverse event may include fatal overdose among participants in the clinical trial. Overdose fatalities in Rhode Island are at crisis levels. Therefore, we may reasonably expect an outcome of fatal overdose among some participants. Given the severity of such an event, the PI will also monitor for self-reported, nonfatal overdoses (at follow-up visits). Each self-reported or fatal overdose will qualify for review by the DSMB to ensure any overdoses among our participants are not related to their participation in the research and are not more prevalent than expected (see below: *Collection and Reporting of Adverse Events [AE] and Severe Adverse Events [SAEs]*). All fatal overdose events occurring in the state are certified by the Office of State Medical Examiners within 90 days. To ascertain fatal overdose events, we will obtain consent from participants at the start of the trial to link to overdose surveillance datasets with participant data using a probabilistic linkage with the following combination of identifiers: first and last name, date of birth, and sex.

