#### Assessing intervention efficacy in reducing fatal and nonfatal overdose (Aim 1, primary endpoint).

The primary outcome will be **non-fatal overdose**, defined as a composite outcome, consisting of one of the following:

1. A self-reported overdose ascertained at the six and/or 12 month follow-up visits;
2. A non-fatal opioid overdose identified in the Rhode Island EMS database, using a case definition for suspected overdose developed by RIDOH previously;
3. An emergency department encounter for an accidental drug overdose that did not result in death, using a case definition developed by the CDC;

The primary analysis will be conducted using a survival framework, with time to *first* nonfatal overdose—identified through any of the data sources noted above—serving as the primary outcome. For self-reported data, event times will be estimated from SAE reports (in which participants are asked to estimate the date of their overdose). Participants will be right-censored as of the date of the first

---

 <https://www.ncbi.nlm.nih.gov/pmc/articles/PMC7948191/>

outcome event or at the end of the follow-up period, defined as 15 months following the participant's baseline visit.

To account for potential imbalance and to improve statistical efficiency, we will adjust for known or anticipated prognostic variables measured at baseline. These variables will include sociodemographic characteristics (e.g., age, gender identity, race/ethnicity), recent criminal justice involvement, housing instability, and substance use patterns including injection drug use & history of overdose. Variables will be transformed or categorized as necessary to address skewed or imbalanced data. We will also adjust for pre-baseline EMS runs for suspected opioid overdoses and ED encounters for drug overdoses using the case definitions noted above, occurring up to six months prior to the date of the participant's baseline visit.

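### Linkage consent is placed after the arm is known in one section and at the start of the trial in another, and the SAP has no rule for unlinked participants

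*Protocol*

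**What the plan says.** **Timing of linkage consent.** Protocol section 3.1e says that, following the baseline survey, "a separate consent procedure will be used to gain permission to obtain information regarding overdose events". A parenthesis adds that this procedure will be submitted as a later amendment once the health department approves. The Data and Safety Monitoring Plan (Attachment F, section E1), discussing how fatal overdoses will be found, says: "we will obtain consent from participants at the start of the trial to link to overdose surveillance datasets".

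**When the arm becomes known.** Protocol section 3.1d: "Randomization will be assigned during the baseline visit". Assessment staff "will be blinded to intervention assignment until completion of the STUDY ENROLLMENT INFORMED CONSENT FORM", and allocations are "revealed only through REDCap by prompts during the baseline survey visit and post-baseline visits". In Attachment A, the opening screen of the baseline survey (Section 2a) carries the note "RA SEES ARM ASSIGNMENT", and the arm-specific session (Sections G and H) is delivered inside that survey. SAP section 1 gives a slightly different order: assessment battery first, then randomization.

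**What depends on linkage.** In SAP section 3 (Aim 1) the primary outcome is time to first nonfatal overdose from any of three sources: self-report at 6 or 12 months, "A non-fatal opioid overdose identified in the Rhode Island EMS database", and an ED encounter. Follow-up ends 15 months after baseline for everyone. The model adjusts for EMS and ED overdose events in the six months before baseline. The exploratory severe endpoint (EMS run, ED encounter or overdose death) comes entirely from linked records.

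**Missing data.** The same section sends missing covariates to multiple imputation, in wording that also mentions a missing outcome. Its one specific missing-outcome rule concerns missing self-report. Participants without linkage are not mentioned.

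**The concern.** Permission to link, if asked for after the arm is known, is a post-randomization variable. It is sought by someone who knows the allocation from someone who has just received either the test-strip session or the control training. Willingness to agree could then differ by arm, and so could the completeness of two of the three primary components, the whole severe endpoint and the pre-baseline EMS and ED history.

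The SAP's silence compounds this. Self-report is collected at 6 and 12 months, but everyone is followed to 15 months. An unlinked participant last seen at the 12-month visit has no data source after that visit. Read literally, the common 15-month limit would leave that person at risk and event-free on the EMS and ED sources. The SAP's concordance check also uses the linked endpoints as the benchmark for missing self-report, which presumes that linkage itself is complete.

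**Working it through.** **1. Order of events.** Three descriptions place allocation differently: Attachment A, Section 1d has it generated after screening and passed to the survey; Protocol 3.1d assigns it during the baseline visit; SAP section 1 puts it after the assessment battery. In all three it precedes the end of the baseline survey, because the survey contains the arm-specific session. A consent step after the survey therefore follows disclosure of the arm to both parties. A step at the start of the trial could precede it. The two placements are not equivalent.

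**2. The plan's own figure.** No figure in the documents concerns linkage. The nearest is the primary power statement (SAP section 6): 250 per arm, 80% retention, 20% v 10%, two-sided 0.05, power above 80%.
- n = 250 × 0.80 = 200 per arm; mean proportion 0.15.
- Power = Φ[(0.10 − 1.96 × √(2 × 0.15 × 0.85/200)) / √((0.20 × 0.80 + 0.10 × 0.90)/200)] = Φ[(0.10 − 0.0700)/0.0354] = Φ(0.849) = 0.802. This reproduces.

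**3. Linked-only (severe) endpoint, illustration.** Inputs: control rate of 8 per 100 person-years, taken as 8% over 12 months; 4% under the planned halving; 250 per arm (SAP section 6). Assumptions: linkage of 80% to 95%, and unlinked people treated as event-free. Observed risk ratio = true risk ratio × (linkage in intervention arm / linkage in control arm).

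| Linkage, intervention v control | True ratio 1.00 becomes | True ratio 0.50 becomes |
|---|---|---|
| 80% v 90% | 0.80/0.90 = 0.889 | 0.444 |
| 85% v 95% | 0.85/0.95 = 0.895 | 0.447 |
| 95% v 85% | 0.95/0.85 = 1.118 | 0.559 |
| 90% v 80% | 0.90/0.80 = 1.125 | 0.562 |

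- False-positive rate with no true effect, 80% v 90%: observed proportions 0.064 and 0.072; standard error √(2 × 0.068 × 0.932/250) = 0.0225; shift 0.008/0.0225 = 0.355 standard errors. The two-sided rejection probability rises from 0.05 to 0.065.
- Equal linkage in both arms leaves the ratio unchanged and costs power. By the formula in step 2, 8% v 4% gives 0.469 with full linkage, 0.449 at 95%, 0.429 at 90% and 0.387 at 80%. The starting value is well below the 80% that the SAP states for this endpoint; that is a separate matter.

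**4. Primary composite, illustration.** Further assumptions: retained participants (r = 0.80) self-report every overdose, and linkage finds 38% of the rest (the SAP's share, a = 0.38) if the person is linked (probability c). Share of events captured = r + (1 − r) × a × c.
- c = 0.80: 0.80 + 0.20 × 0.38 × 0.80 = 0.8608.
- c = 0.90: 0.80 + 0.20 × 0.38 × 0.90 = 0.8684.
- Ratio under no effect: 0.8608/0.8684 = 0.991; reversed, 1.009.
- 85% v 95% gives 0.8646/0.8722 = 0.991.

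**The case against.** The strongest reply is that the SAP nowhere says that unlinked people count as event-free or as having no overdose history. A reader might infer both from the common 15-month limit, but the documents do not support stating either as the plan. For history, the text points the other way: a covariate that could not be obtained is missing, and missing covariates go to multiple imputation. The imputation wording also mentions a missing outcome. What stands is narrower: that wording names no linked source, the specific outcome rule covers self-report only, and no censoring rule exists for people without linkage.

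Second, section 3.1e describes a procedure still to be written, and the consent forms are not among the pages available here, so the final placement cannot be checked. That is fair, but the placement after the survey is the current text, and it disagrees with the monitoring plan.

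Third, a reader might infer that the monitoring plan already puts linkage consent in the enrollment form ahead of allocation. It does not. It says only that consent comes at the start, mentions neither the form nor the arm, and is written about fatal overdose.

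Fourth, no decline rate or difference by arm is documented, so every ratio in the illustration is conditional. That stands in full.

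**Conclusion.** The point holds as a conflict between two current texts on when linkage consent is taken, together with a gap in the SAP. Under section 3.1e, linkage becomes a choice made after the arm is known, and the SAP does not say what happens to those who decline or are never asked.

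The size is hypothetical. A 10-point difference in linkage between arms would move a null ratio on the linked-only endpoint by roughly 11% to 13% in either direction, and only if unlinked people were treated as event-free. The SAP labels that endpoint exploratory. A reader might infer that the primary result is equally exposed. The documents do not support that: self-report remains a source, death is not a primary component, and the same difference moves the primary ratio by under 1%. That last figure assumes complete self-report among retained participants and would grow if they under-report.

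The change is worth making because it is cheap and closes a route to bias, not because a material distortion has been shown.

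**What to change.** **Protocol.** Amend section 3.1e so that linkage consent is sought before the arm is displayed, make section E1 of the monitoring plan say the same for fatal and nonfatal events, and record linkage-consent status and date for every participant.

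**SAP.**
- Report linkage status by arm.
- Treat absent linkage as missing, not zero, for outcomes and for pre-baseline history. For example, in the primary analysis censor unlinked participants at their last self-report assessment and impute their EMS and ED history. Name the linked sources in the imputation model for the severe endpoint.
- Compute the self-report concordance among linked participants only.
- Keep all randomized participants in the main analysis. For anyone asked after the arm was known, a consenters-only analysis conditions on a post-randomization choice, so it belongs among the sensitivity analyses.

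**Cost.** A small change in consent order, one data field and a short SAP paragraph. Censoring at the last self-report assessment assumes that the censoring is uninformative given the covariates. The change cannot repair the order for people already enrolled; for them, recorded status and date by arm at least make the problem visible.
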